1.4. Glossary

Term	Definition
AE	Adverse Event
ADE	Adverse Device Effect
ADL	Activities of Daily Living
ANZ	Australia and New Zealand
AP	Anterior-Posterior view
CEC	Clinical Event Committee
CIP	Clinical Investigation Plan
CTA	Clinical Trial Agreement
CV	Curriculum Vitae
EC	Ethics Committee
ECG	Electrocardiogram
Ethics Committee	Term that will be used collectively in reference to an Institutional Review Board (IRB)/Medical Ethics Committee (MEC)/Human Research Ethics Committee (HREC)/Research Ethics Board (REB)/Ethics Committee (EC) unless otherwise stated
E-CRF	Electronic Case Report Form
EDC	Electronic Data Capture
EGM	Electrogram
EV ICD	Extravascular Implantable Cardioverter Defibrillator
GCP	Good Clinical Practice
IB	Investigator's Brochure
IC	Informed Consent
ICD	Implantable Cardioverter Defibrillator
ICF	Informed Consent Form
INR	International Normalized Ratio
IRB	Institutional Review Board
ISF	Investigator Site File
LAT	Lateral view
NOAC	Novel Oral Anticoagulant
PSA	Pacing System Analyzer
PVT	Polymorphic Ventricular Tachycardia
SAE	Serious Adverse Event
SADE	Serious Adverse Device Effect
SC	Steering Committee
SSVA	Sustained Shockable Ventricular Arrhythmia
USADE	Unanticipated Serious Adverse Device Effect
Zone 1	Tunneling and deployment of the lead in the substernal space
Zone 2	Tunneling of the lead from the sternum to the device pocket

2. Synopsis

Title	Extravascular Implantable Cardioverter Defibrillator (EV ICD) Pilot Study
Clinical Study Type	Pilot
Product Name	
System Components:
 
 • Medtronic Model DVEX2E4 EV ICD • Medtronic Model EV2401 EV ICD Lead 
Accessory Components:
 
 • Medtronic Model EAZ101 Sternal Tunneling Tool • Medtronic Model EAZ201 Transverse Tunneling Tool • SafeSheath II, model number SSCL9 • Medtronic 2090 CareLink Programmer with EV ICD SW041 Programmer Software Version 8.0 (or greater) installed 
Equipment:
 
 • DR220 Holter Recorder
Sponsor	
Medtronic Inc. [name] [contact]

Local Sponsor	
Medtronic Australasia Pty Ltd [name] Australia [contact]
 
Medtronic New Zealand Limited [name] New Zealand [contact]

Indication under investigation	The Medtronic EV ICD system (defibrillator and lead) is indicated to provide ventricular antitachycardia pacing and ventricular defibrillation for automated treatment of life-threatening ventricular arrhythmias in patients who do not have symptomatic bradycardia.
Investigation Purpose	The main purpose of the EV ICD Pilot study is to characterize the preliminary safety and efficacy of the EV ICD system. The use of a pilot

EV ICD Pilot Study Clinical Investigation Plan

MDT17034

Version 1.0, 02-MAR-2018 Page 12 of 133

Medtronic

	study design allows characterization of the EV ICD system in a limited number of subjects before launching into a large-scale pivotal study.
Product Status	
Components that are considered investigational:
 
• Medtronic Model DVEX2E4 EV ICD• Medtronic Model EV2401 EV ICD Lead• Medtronic Model EAZ101 Sternal Tunneling Tool• Medtronic Model EAZ201 Transverse Tunneling Tool• Oscor SafeSheath II Model SSCL9• DR220 Holter Recorder 
Components that are considered market-released:
 
• Medtronic CareLink 2090 Programmer with investigational programmer Software SW041 version 8.0 (or greater)
Primary Objective(s)	
Primary Safety Objective: Characterize the freedom from major complications related to the EV ICD system and/or procedure at 3-months post-implant
 
Primary Efficacy Objective: Characterize the EV ICD defibrillation testing success rate at implant

Ancillary Objective(s)	
• Characterize appropriate and inappropriate shocks• Characterize electrical performance (pacing capture thresholds, pacing impedance, sensing amplitudes) in a variety of postures and respiration cycles over time• Characterize pacing sensation• Characterize asystole pacing• Characterize lead position over time• Summarize ATP performance with spontaneous arrhythmias• Summarize adverse events
Study Design	
The EV ICD Pilot Study is a prospective, multi-center, single-arm, non-randomized Study. Up to 35 subjects will be enrolled at up to 10 sites in Australia and New Zealand.
 
Subjects indicated for single-chamber ICD therapy will be recruited and implanted with the Medtronic EV ICD system. Subjects will undergo assessments at Pre-Hospital Discharge, 2 Weeks, 4-6 Weeks and 3 Month Visits. Subjects will subsequently be followed up at 6-Months post-implant and every 6 months thereafter until study closure.

Sample Size	
20-35 enrollments (worldwide)
 
Maximum number of subjects undergoing an implant attempt will be capped at 9 per site.

Medtronic Confidential

056-F275, v3.0 Clinical Investigation Plan Template

Inclusion/Exclusion Criteria
	
Inclusion Criteria
 
 1) Patient has a Class I or IIa indication for implantation of an ICD according to the ACC/AHA/HRS Guidelinesⁱ 2) Patient is willing and able to sign and date the Informed Consent Form. 3) Patient is at least 18 years of age and meets age requirements per local law 4) Patient is geographically stable and willing and able to comply with the study procedures and visits for the duration of the follow-up 
Exclusion Criteria
 
 1) Patient has indications for bradycardia pacingⁱⁱ or Cardiac Resynchronization Therapy (CRT)ⁱⁱⁱ (Class I, IIa, or IIb indication) 2) Patient has an existing or had a prior pacemaker, ICD, or CRT device implant or leads 3) Patient has anatomical abnormality that significantly increases implant risk^{iv} including: 
 ○ Severe obesity^v ○ Marked RV dilation ○ Marked sternal abnormality ○ Hiatus hernia that distorts mediastinal anatomy 4) Patient has prior chest radiotherapy 5) Patient had previous mediastinitis 6) Patient had previous coronary artery bypass grafting procedure 7) Patient has existing transcatheter aortic valve replacement 8) Patient has gastrostomy tube
--	---

i Al-Khatib SM, Stevenson WG, Ackerman MJ, Bryant WJ, Callans DJ, Curtis AB, Deal BJ, Dickfeld T, Field ME, Fonarow GC, Gillis AM, Hlatky MA, Granger CB, Hammill SC, Joglar JA, Kay GN, Matlock DD, Myerburg RJ, Page RL. 2017 AHA/ACC/HRS guideline for management of patients with ventricular arrhythmias

ii 2015 HRS/EHRA/APHS/SOLAECE expert consensus statement on optimal implantable cardioverter-defibrillator programming and testing).

iii ACC/AHA/HRS guidelines for Cardiac Resynchronization Therapy

iv Per physician discretion

v BMI > 40

	
9) Patient has had a prior sternotomy, prior mediastinal instrumentation, prior abdominal surgery in the epigastric region, or planned sternotomy
 
10) Patient has previous pericarditis that:
 
 ○ Was chronic and recurrent, or ○ Resulted in pericardial effusion ^{vi}, or ○ Resulted in pericardial thickening or calcification ^{vii} 
11) Patients with a medical condition that precludes them from undergoing defibrillation testing, such as:
 
 ○ known LV thrombus ○ decompensated heart failure ○ LVEF <20% ^{viii} ○ other physician discretion 
12) Patient has persistent Atrial Fibrillation who is at high risk of a thromboembolic event with a CHA₂DS₂-VASc score ≥3, or is contraindicated for having anticoagulation interrupted for ≥72 hours
 
13) Patients with comorbidities which may increase surgical risk of complications^{ix} including:
 
 ○ severe aortic stenosis ○ COPD and is oxygen dependent ○ Hepatosplenomegaly ○ Marked hepatomegaly 
14) Patient is on renal dialysis
 
15) Patient with any evidence of active infection or undergoing treatment for an infection
 
16) Patient with current implantation of neurostimulator or any other chronically implanted device which uses current in the body.
 
17) Patients with a limited life expectancy of less than 12 months
 
18) Patient is enrolled or planning to enroll in a concurrent drug or device study that may confound the results of this

--	--

vi As documented on echo or MRI

vii As documented on CT scan or MRI

viii Most recent LVEF in the last 180 days (inclusive)

ix Per physician discretion

EV ICD Pilot Study Clinical Investigation Plan

MDT17034

Version 1.0, 02-MAR-2018 Page 15 of 133

	
study, without documented pre-approval from a Medtronic study manager
 
19) Patient with any exclusion criteria as required by local law (e.g., age, pregnancy, breast feeding)
 
20) Pregnant women or breastfeeding women, or women of child bearing potential and who are not on a reliable form of birth regulation method or abstinence ^x

Study Procedures and Assessments
	
Once enrolled, a subject will be assessed at the following visits:
 
 • Baseline • Implant • Pre-Hospital Discharge • 2 Weeks • 4-6 Weeks • 3 Months • 6, 12, 18, 24... Months 
Study procedures are outlined in the table below.

Study procedure	B/L	IMP	PHD	2 WKS	4-6 WKS	3 MO	6, 12, 18, 24... MO	U'SCH	SYS MOD	EXT
Informed Consent	X									
Inclusion/Exclusion Assessment	X									
Physical Exam, Demographics, Cardiovascular Medical History	X									
Surface ECG	X*	X [†]							X [^]	
Surgical history	X									
System and procedure information		X							X	
Fluoroscopy recordings during tunneling procedure		X							X [^]	
Fluoroscopy (AP and Lateral) of final ICD generator and lead position (cine preferred)		X							X [^]	
On site ECG monitoring (DR220 Holter)		X	X	X	X	X			X [^]	
Sensing, Impedance & Pacing Tests		X					X		X [^]	
Defibrillation Testing		X							X [^]	
Provocative testing (postures): (Sensing, Impedance and Pacing tests)			X	X	X	X				
Provocative Testing (Maneuvers)			X	X	X	X				
Provocative Testing – brisk walk				X	X					
Provocative Testing – Regular Treadmill						X				
Cardiac-gated CT	X					X (w/o contrast)				
Radiographs – Standing and Supine, AP & LAT, tidal Inhalation and Exhalation			X		X	X				
Echocardiogram	X*		X							

x if required by local law, women of child-bearing potential must undergo a pregnancy test within seven days prior to EV ICD Pilot Study procedures

EV ICD Pilot Study Clinical Investigation Plan

MDT17034

Version 1.0, 02-MAR-2018 Page 16 of 133

24-hour Holter Monitoring (DR220 Holter)					X	X				
Pocket/ incision photographs			X	X	X	X	X [#]	X [#]	X	
Save-to-media files		X	X	X	X	X	X	X	X	
Medications	X	X	X	X	X	X	X	X	X	X
Adverse Events (including AEs with fatal outcome), Device Deficiencies, Study Deviations, Other Imaging, and Subject Exits		As they occur								

* Within 30 days prior to consent is acceptable [†] If available, collected through EP recording system during procedure [#] Recommended if infection related to the EV ICD System is suspected [^] System modification where a subject leaves with an EV ICD System
										
Safety Assessments	All Adverse Events that are procedure related, system related, accessory related, Holter related, cardiovascular related, or serious that occur from the time of enrollment through study exit will be collected and reported to Medtronic during the study. Additionally, any device deficiency related to the EV ICD System will be collected.									
Statistics	Descriptive statistics will be used to summarize all endpoints. For some endpoints such as lead position and pacing testing, multiple measurements per subject will be assessed and compared.									

3. Introduction

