8.8.5. Imaging (4-6 Weeks, 3 Months)

8.8.5.1. Radiographs and CT Scans

Cardiac-gated CT scan (respiratory cycle for CT: tidal inhalation only) is to be performed during the 3 Month follow-up visit. Contrast is not required. It is recommended that prospective gating (best diastole phase of the cardiac cycle) be used to reduce radiation dose to the subject.

- The CT image should include the thorax from the collarbone to the inferior aspect of the ribcage and include the entire width of the torso, i.e., side-to-side, and the implanted ICD device.
- The slice thickness should be ≤ 1.2 mm (≤ 0.8 mm preferred).
- The in-plane resolution should be ≤ 0.7 mm (≤ 0.5 mm preferred).

All radiographs will be collected in the anterior-posterior (AP) and lateral (LAT) configurations as specified in Table 8.

Additional radiographs may be collected at the discretion of the physician in additional postures (i.e. prone, left decubitus, right decubitus) at any post-implant time point if electrical testing at follow-up reveals deterioration in sensing or pacing performance. Additional imaging at different postures is recommended if:

- Pacing output changes by 3V in magnitude in either direction (pacing testing performed in 1V increments); or
- R-wave amplitude falls below 1mV, or falls by 50% of previous measurement.

Table 8: Image collection during follow-up period.

Visit	Image Collection
4-6 Weeks	
 • Supine AP → Tidal Inhalation and Tidal Exhalation • Supine LAT → Tidal Inhalation and Tidal Exhalation • Standing AP → Tidal Inhalation only • Standing LAT → Tidal Inhalation only
3 Months	Cardiac-gated CT (no contrast) (Respiratory cycle for CT: tidal inhalation only)
	
 • Supine AP → Tidal Inhalation and Tidal Exhalation • Supine LAT → Tidal Inhalation and Tidal Exhalation • Standing AP → Tidal Inhalation only • Standing LAT → Tidal Inhalation only

All images should be transferred in DICOM format.

If additional images (CT scans, radiographs, TEE, MRI or other imaging modalities) are collected at physician discretion throughout the duration of the study, it is requested that a copy of the images be sent to Medtronic.

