### 7.2 General Methodology

Data analysis will be performed by a Medtronic statistician or designee.

All analyses will be performed on an “As Treated” basis. The cohort will include all enrolled subjects who undergo the study procedures, and there are no prespecified subgroups for assessment. For endpoints involving only measurements collected at follow-up visits, only subjects who complete those visits will be included in the analysis of those endpoints.

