## 7.9.4 Ancillary Objective #2

Characterize electrical performance (pacing capture thresholds, pacing impedance, sensing amplitudes) in a variety of postures and respiration cycles over time.

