### 7.9.4.2 Performance Requirements

Performance requirements are not pre-specified for this objective. The endpoints are defined as pacing capture threshold, pacing impedance, and sensing amplitude. The pacing testing will be performed at pre-hospital discharge, as well as visits at 2 weeks, 4-6 weeks, and 3 months post-implant.

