### 7.9.4.4 Analysis Methods

Results will be summarized in aggregate using descriptive statistics. Pacing testing will be done at the postures provided in section 8.8.4.1. For each posture, and each follow-up visit, the proportion of subjects undergoing pacing testing will be reported, as well as the proportion for whom capture is obtained.

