## 7.9.7.4 Analysis Methods

Imaging (radiographs) will be performed at pre-hospital discharge, as well as visits at 4-6 weeks and 3 months. Lead position will be assessed and degree of movement will be summarized for each subject.

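### No within-subject summary is specified for pacing capture or sensing over time, although the synopsis says repeated pacing measurements per subject will be compared

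*Protocol*

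**What the plan says.** The Statistics entry of the protocol synopsis covers two endpoints: "For some endpoints such as lead position and pacing testing, multiple measurements per subject will be assessed and compared".

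For lead position, SAP 7.9.7.4 provides a subject-level result: "degree of movement will be summarized for each subject".

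For pacing and sensing, the objective in SAP 7.9.4 is to "Characterize electrical performance (pacing capture thresholds, pacing impedance, sensing amplitudes) in a variety of postures and respiration cycles over time". SAP 7.9.4.2 adds: "The endpoints are defined as pacing capture threshold, pacing impedance, and sensing amplitude". The method in SAP 7.9.4.4 begins: "Results will be summarized in aggregate using descriptive statistics. Pacing testing will be done at the postures provided in section 8.8.4.1". It then names two outputs for each posture and follow-up visit: the share of subjects tested, "as well as the proportion for whom capture is obtained". Protocol 12.6.4 says the same. Neither section mentions a change within a subject, a paired table or a shift table.

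The subjects behind each figure can differ:
- SAP 7.2 says that for follow-up measurements "only subjects who complete those visits will be included in the analysis of those endpoints".
- SAP 7.9.4.5 admits a subject who has pacing tests in a single posture.
- Protocol 8.7.3 makes posture testing at discharge depend on the subject's ability, and Protocol 8.8.4 does not count a posture that cannot be performed as a deviation.

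The protocol already contains limits for change, used to prompt extra imaging. In 8.7.4 and 8.8.5.1 they are a 3 V change in pacing output in either direction, and, in the words of 8.8.5.1, "R-wave amplitude falls below 1mV, or falls by 50% of previous measurement".

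**The concern.** The objective concerns behaviour over time, and Protocol 8.8 gives electrical stability as a purpose of the follow-up electrical testing. Stability belongs to the individual subject: did someone who captured or sensed adequately at discharge stop doing so later? Protocol 9.4 lists dislodgement in the absence of fibrosis among the risks particular to a chronic substernal lead, so this is a natural question for a first chronic implant series.

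A row of capture proportions by visit does not answer it. Equal proportions may mean that nobody changed, or that some subjects lost capture while others gained it. A difference between visits may partly reflect who was tested. According to Protocol 5.2, the pilot data are meant to guide programming in the pivotal study. A report that cannot state how many subjects lost capture or sensing serves that purpose less well than the collected data would allow.

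**Working it through.** **Figure to reproduce.** There is none. The objective has no hypothesis (SAP 7.9.4.1), and the sample size is not derived from a test (SAP 6).

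**Inputs.** The number implanted is 20 to 35 (SAP 6). The documents give no expected capture rate by posture, so rates from about 70% to 95% are assumed to show the range.

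**Capture.** Let the same n subjects be tested at two visits, with a capturing at the earlier and b at the later. The number L who lost capture satisfies

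max(0, a − b) ≤ L ≤ min(a, n − b).

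The upper limit holds because nobody can lose capture who did not have it, and every loss is among the n − b without capture later.

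| n | captured, earlier → later | possible losses | maximum as share of a |
|---|---|---|---|
| 20 | 19 → 19 | 0 to 1 | 1/19 = 5.3% |
| 20 | 18 → 18 | 0 to 2 | 2/18 = 11.1% |
| 20 | 16 → 16 | 0 to 4 | 4/16 = 25.0% |
| 20 | 14 → 14 | 0 to 6 | 6/14 = 42.9% |
| 35 | 33 → 33 | 0 to 2 | 2/33 = 6.1% |
| 35 | 32 → 32 | 0 to 3 | 3/32 = 9.4% |
| 35 | 28 → 28 | 0 to 7 | 7/28 = 25.0% |
| 35 | 24 → 24 | 0 to 11 | 11/24 = 45.8% |

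A net rise does not exclude losses. From 16/20 to 17/20, L can be 0 to min(16, 3) = 3. From 28/35 to 30/35, it can be 0 to min(28, 5) = 5.

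**Changing denominators.** The bounds above assume the same subjects at both visits. Suppose instead that 20 are implanted and 16 are tested in a posture at each visit (assumed). The number tested at both then lies between 16 + 16 − 20 = 12 and 16. The share tested is reported, but the overlap is not, so even the number of pairs is unknown.

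**Sensing.** The capture proportions say nothing about sensing, which falls under the general sentence on descriptive statistics. Assumed example: 20 subjects have an R-wave of 3.0 mV; later, 2 are at 0.8 mV, 2 at 5.2 mV and 16 unchanged. The later mean is (2 × 0.8 + 2 × 5.2 + 16 × 3.0)/20 = 60/20 = 3.0 mV and the median is 3.0 mV, yet 2 subjects are below 1 mV. A reported minimum would show 0.8 mV, but not how many fell or from what level. Protocol 8.8.3.1 also allows another sensing vector when the R-wave drops below 1 mV. If amplitude is summarised in the programmed vector, which the SAP does not state, a replaced vector leaves the summary.

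**The case against.** The strongest reply is that the plan is less bare than it looks and that little depends on it.

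- SAP 7.9.4.4 opens with a general descriptive summary, which covers capture threshold, impedance and sensing amplitude. A reader might infer that capture proportions are all that will be reported; the text does not support that. This stands. But the summary is specified as aggregate, so individual change remains undetermined.
- A reader might infer that losses will go unnoticed. They will not. SAP 7.4 puts all available data in the listings, and with 20 to 35 subjects each series can be read. Protocol 8.8.3.1 has sites evaluate other vectors when an R-wave is below 1 mV and consider imaging and system modification if that level cannot be maintained. A related complication leading to system revision enters the primary safety endpoint. This also stands: the gap is in the planned summary, not in the data or in subject care.
- A reader might infer that the SAP dropped a protocol analysis. SAP 7.9.4.4 repeats Protocol 12.6.4, so the mismatch is between the synopsis and both methods sections. The synopsis also names no paired statistic or pair of visits. It does speak of several measurements per subject being compared, and the methods sections name nothing that does so for pacing.
- A reader might add that unpaired summaries waste precision. With no hypothesis and no standard error or interval planned for a change, that argument has no place here.
- The 3 V limit runs in both directions and only prompts imaging. It should not be read as a definition of deterioration.

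**Conclusion.** The point holds as a gap in specification. The synopsis announces a comparison of repeated pacing measurements per subject. The methods sections name only aggregate outputs, from which the number of subjects who lost capture or adequate sensing cannot be derived. Under the assumed rates, the undetermined number is up to 4 of 20 or 7 of 35 at 80% capture, and up to 1 of 20 or 2 of 35 at about 95%. Protocol 3.1 reports from acute testing that pacing should be possible in nearly all patients. If that carries over to every posture and visit, the range will be narrow; the documents do not show that it does.

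The finding concerns one of seven ancillary descriptive objectives. No primary result, decision rule or sample size is affected. A paired table answers the stated objective better than the named outputs do, at very little cost.

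**What to change.** Add the following to SAP 7.9.4.4 and Protocol 12.6.4, in subjects measured at both times, by posture and by pacing or sensing vector:

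1. A cross-table of capture at pre-hospital discharge against each later visit: kept, lost, gained, never captured.
2. The within-subject change (median, range) in capture threshold, impedance and R-wave amplitude.
3. The number whose pacing output rose by 3 V or more and, separately, the number whose output fell by 3 V or more; and the number whose R-wave fell by 50% or to below 1 mV, noting any change of sensing vector. State the reference reading, because the 50% limit in Protocol 8.8.5.1 refers to the previous measurement.

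Pairing by vector matters because Protocol 8.6.6.3 and 8.8.3.3 allow three pacing configurations and the sensing vector may be switched; otherwise different electrode pairs would be mixed. Keep discharge as the reference, since posture testing starts there, and footnote that prone may be simulated at that visit (Protocol 8.8.4.1). Implant readings may be shown separately but not as time zero: Protocol 8.6.3 strongly recommends general anaesthesia for the procedure, so they are not comparable with awake readings.

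The cost is SAP and protocol wording plus some descriptive tables. With six postures and three later visits, the capture table has 6 × 3 = 18 rows per vector. No new visit or test is needed. Paired denominators will be smaller than the per-visit ones, so show both.
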